#### **2.4. Impact of bone marrow microenvironment on sensitivity to retinoids:**

APL and most non-APL AMLs undergo terminal differentiation and elimination by ATRA *in vitro*. However, as mentioned above, ATRA has not proven effective in non-APL AML in randomized clinical trials to date (Burnett et al., 2010; Burnett et al., 2007; Estey et al., 1999; Milligan et al., 2006). Retinoic acid (RA) plays a significant role in the differentiation of hematopoietic stem cells (HSCs). Recent data from our group show that the cytochrome P450 enzyme CYP26 expressed in bone marrow (BM) stromal cells inactivates RA, thereby limiting differentiation of HSCs ([name] et al., 2013). We have also shown that several APL and non-APL AML cell lines are sensitive to RA-induced differentiation and elimination *in vitro*, but this was prevented in the presence of BM stroma; addition of the CYP26 inhibitor R115866 reversed stroma-induced resistance to RA (Su et al., 2015). Use of R115866 in a clinical trial is not possible due to lack of availability.

A second strategy is to use a retinoid resistant to metabolism by CYP26. IRX5183 and AM80 are synthetic retinoids resistant to CYP26 metabolism, 10 times more potent than ATRA as *in vitro* inducers of differentiation in APL cells, and have been studied clinically to treat APL and other malignancies (Osanaï & Petkovich, 2005; Sanford D, 2014). IRX5183 is more selective for retinoic acid receptor alpha than AM80, potentially leading to a milder side effect profile. Preliminary clinical experience with IRX5183 in a phase I/II study in solid tumor patients showed the drug was well tolerated without any serious adverse events; it has also been used in a few patients with newly diagnosed APL (company data). Data from our laboratory show that both AM80 and IRX5183 are resistant to stroma-mediated inactivation, similar to the

combination of ATRA and R115866.

## 2.5. **IRX5183:**

IRX5183 is a synthetic retinoid produced by Io Therapeutics, Inc. that specifically targets retinoic acid receptor alpha (RAR $\alpha$ ). Understanding of the function of the retinoid family of receptors is crucial for comprehension of the function of IRX5183 in treatment of AML. Although an extensive review is beyond the scope of this protocol background, the general principles in retinoid acid receptors are discussed below. In general, retinoic acid receptors (RARs) and retinoid X receptors (RXRs) are ligand-dependent transcription factors that are a part of the steroid/thyroid family. RARs play an important role in the differentiation and growth regulation of many adult tissues, especially hematopoiesis, with 6 different domains involved in constitutional transcript activation, DNA binding, ligand binding, dimerization, and ligand-induced transcriptional activation (Morosetti et al., 1996). Metabolites of Vitamin A bind to the RARs but do not bind to the RXRs. The RARs and RXRs have integrated function and alter gene transcription based on their dimerization either as homodimers or heterodimers (Morosetti et al., 1996). An example of the interaction between the RARs and RXRs and treatment with retinoids that bind the RARs is seen with all-trans retinoic acid (ATRA) for acute promyelocytic leukemia. The overwhelming success of ATRA inducing terminal differentiation of blasts in APL is an example of use of agents that affect the RARs and RXRs that is now the standard of care for treatment of APL.

ATRA is known to target RAR $\alpha$ ,  $\beta$ , and  $\gamma$  at pharmacologic concentrations, but only RAR $\alpha$  and  $\gamma$  are expressed in immature and maturing hematopoietic cells. Preclinical studies by Chee et al suggested that ATRA enhances hematopoietic stem cell self-renewal through RAR $\gamma$ , while promoting differentiation of committed myeloid progenitors through RAR $\alpha$  activation (Chee, Hendy, Purton, & McArthur, 2013). They found that IRX5183 decreased clonogenicity and increased mature myeloid markers by flow in AML1-ETO-expressing murine BM progenitors *in vitro*, whereas ATRA had the opposite effect (potentiation of clonogenicity and immature myeloid phenotype by flow), suggesting the efficacy of a RAR $\alpha$  specific agent in non-APL AML. In addition to being a pan-RAR agonist, ATRA is known to induce CYP26 expression, which likely impacts its bioactivity (Ozpolat, Mehta, Tari, & Lopez-Berestein, 2002). In contrast, metabolism studies in liver microsomes from multiple species, including human, indicate that IRX5183 is not subject to oxidative metabolism (Investigator's Brochure, 2008).

Unlike other retinoids with pan RAR activity, IRX5183 did not induce dermal irritation in a mouse model. However, it does retain the hypertriglyceridemic effect of other retinoids. A receptor-specific retinoid such as IRX5183 may induce fewer adverse effects when compared to a receptor-non-specific retinoid such as ATRA, while retaining the modulation activity of the cell cycle. The clinical use of ATRA has been complicated by the development of ATRA resistance due to pharmacokinetic reasons. Chronic oral ATRA therapy in APL patients results in progressively lower blood levels of ATRA presumably because of autoinduction of metabolism (Adamson, 1996). In contrast, structural features incorporated into the IRX5183 molecule have been designed to make the compound resistant to this degradative catabolism. Full pharmacokinetic evaluation in rats demonstrates that, for the most part, maximal concentrations (Cmax) and area-under-the-curve (AUC) values are not changed between days 8 and 30 at any of the doses tested. Similar evaluations in dogs show that IRX5183 Cmax and AUC values are unchanged between days 7 and 28. This pharmacokinetic profile observed in rats and dogs appears to be retained in humans, where Cmax and AUC values on day 14 were increased relative to day 0 after the first dose (Investigator's Brochure, 2008). Therefore, persistently high blood drug levels should be obtained upon chronic oral dosing with IRX5183.

IRX5183 was studied in an animal model of t(8;21) AML1-ETO, where fetal liver cells were transfected and transduced with AML1-ETO9a plasmids and transplanted into irradiated Ptpcr mice (Chee et al., 2013). The mice developed leukemia by 5 weeks post-transplant. IRX5183 or DMSO was given orally at 45 mg/kg daily six days per week for four weeks. The IRX5183 treated mice had significantly lower total white blood cell counts, peripheral blood blasts, and green fluorescent protein positive cells two weeks after completion of treatment. In addition, they had significantly more maturing intermediate myeloid cells and neutrophils. There was no effect on survival of the mice, but treatment ceased after only four weeks of therapy; after drug withdrawal, the blast cell population expanded and ultimately led to death from leukemia.

[figure not shown]
IRX5183 has been used in humans in two separate studies. The first was a single-center, phase I trial evaluating the safety, maximum tolerated dose (MTD), and pharmacokinetics of IRX5183 administered daily for a minimum of 4 weeks, performed in patients with refractory malignancies. The starting dose was 60 mg/m^2/day as a single daily dose in the morning based on pre-clinical data. A total of 15 patients were accrued, and 12 completed at least one 4-week cycle of therapy. Due to dose-limiting toxicities (DLTs), the dose was reduced to 30 and then 15 mg/m^2, with 15 mg/m^2 determined to be the MTD. 3 of 4 DLTs were elevated alkaline phosphatase (all in patients with liver metastases and 2 had elevated alkaline phosphatase at baseline). The 4th DLT was grade 3 mucosal inflammation. 10 patients came off study because of progressive disease (PD) and no antitumor activity was observed. The drug was absorbed rapidly and reached peak concentrations approximately 1 to 3 hours following dosing. The terminal elimination half-life ranged from 3.3 to 16.1 hours on the first day of dosing. Based on persistently high drug levels, stable anti-proliferative, pro-differentiation and anti-apoptotic effects could be expected with oral IRX5183.

The second trial evaluating IRX5183 in humans was a randomized, open label, single center phase I/II trial studying peripheral blood progenitor cell (PBPC) mobilization in combination with G-CSF, with intra-patient control and an additional control arm of two mobilizations with G-CSF alone, after high dose chemotherapy in patients with multiple myeloma and lymphoma. For the intra-patient control, each patient underwent 2 mobilizations and mobilization variables were compared between each episode. IRX5183 was given at a dose of 60 mg/m^2 daily and G-CSF was given at a dose of 10mcg/kg daily. 8 patients were accrued to the study and patients were administered IRX5183 60 mg/m^2 daily for up to 28 days. No serious adverse events associated with IRX5183 were reported and no DLT was observed. The conclusion from the study was that IRX5183 and G-CSF in combination was unlikely to benefit poor progenitor cell mobilizers, but it may benefit good mobilizers, particularly if pretreated prior to a second mobilization with G-CSF alone.

#### Preclinical studies at Johns Hopkins:

Preclinical studies were conducted in the labs of [name] and [name] at Johns Hopkins Oncology Center. Leukemia cell lines NB4 (an APL cell line with t(15;17)), OCI-AML3 (an AML cell line with NPM1 mutation), and Kasumi-1 (AML cell line with t(8;21)) were used in the experiments. Cells were incubated with control media vs. equal concentrations of ATRA or IRX5183 in the presence and absence of BM stroma. Differentiation was assessed via flow analysis for marker CD11b and clonogenic growth was assessed using a colony forming unit assay. ATRA and IRX5183 showed similar increased differentiation and inhibition of clonogenic recovery compared to control in liquid culture, but in the presence of BM stroma, only IRX retained its efficacy (Figure 1, unpublished data). Therefore, IRX5183 is resistant to inactivation by stromal CYP26.

**Figure 1: Stroma blocks ATRA-mediated, but not IRX5183-induced elimination of AML.** Colony forming unit (CFU) experiments with (A) OCI-AML3 and (B) NB4 cells treated with ATRA or IRX5183 at doses of  $10^{-6}$  and  $10^{-7}$ M for the different cell types, respectively, showed a decrease in clonogenic growth compared to control with IRX5183 both off and on stroma.

We additionally incubated NB4 cells with CD437, a RAR $\gamma$  specific agent that is also resistant to metabolism by CYP26, and this resulted in a complete lack of increase in differentiation markers compared to control and no decrease in clonogenic recovery. Therefore, targeting RAR $\gamma$  had no impact on cellular differentiation. qRT-PCR experiments showed that IRX5183 had minimal impact on CYP26 expression in OP-9 stromal cells, unlike ATRA and CD437, suggesting the impact of RAR $\gamma$  in the marrow microenvironment is induction of CYP26, while targeting of RAR $\alpha$  leads to myeloid differentiation. Moreover, IRX5183 is a RAR $\alpha$  specific agent that is able to bypass metabolism by CYP26 in BM stroma. The demonstrated preclinical data in combination with the successful use of retinoids in APL provides the foundation for the proposed trial.

## 2.6. Rationale:

We postulate that, to date, retinoids have not been proven effective in the treatment of non-APL AML due to stromal protection by CYP26. Our lab has published recently that this mechanism of stromal resistance to cancer therapies is not limited to ATRA. There are a multitude of liver enzymes present in the BM stroma, including CYP3A4, which metabolizes BEX and etoposide, among many other agents, and cytidine deaminase, which metabolizes cytarabine (Alonso et al., 2015). BEX + GM-CSF previously showed some differentiating ability in our phase II trial, but may have not been fully effective due to high CYP3A4 expression. IRX5183 is a novel retinoid, which as a single agent bypasses this mechanism of protection afforded leukemia cells in the BM microenvironment. In addition, its RAR $\alpha$  specificity is attractive as RAR $\gamma$  does not appear to have an effect on differentiation and may lead to additional side effects. The preclinical data with IRX5183 inducing differentiation in leukemia cell lines and the prior *in vivo* mouse model give support for proceeding with a trial of single agent IRX5183 in AML and HR-MDS. In addition, the oral bioavailability, and good tolerance of IRX5183 in solid tumor patients previously make it an attractive agent to study. Given that the phase I trial was in solid tumor patients previously, many with underlying liver dysfunction, we would like to perform a phase I/II trial in order to establish the safety and toxicity profile in patients with AML and MDS. Although there is no current data for the use of IRX5183 in myeloid malignancies to describe the baseline response we expect to see

and function as a control to which our results would be compared, there is a plethora of data with other differentiating agents in myeloid malignancies that can serve as expected control response.

### 3. PATIENT SELECTION

#### 3.1. Eligibility criteria:

The eligibility criteria are as follows:

1. Patients must be able to understand and voluntarily sign an informed consent form.
2. Age  $\geq 18$  years at the time of signing the informed consent form.
3. Able to adhere to the study visit schedule and other protocol requirements.
4. Pathologically confirmed disease with A or B as follows:
  - A. AML patients who either have:
    - 1) Relapsed or refractory disease after receiving one or more courses of induction chemotherapy, hypomethylating agent therapy, or bone marrow transplant *or*
    - 2) *de novo* AML but not deemed to be a candidate for conventional therapy based on age, co-morbidities, or patient preference
  - B. MDS, CMML, or MDS/MPN with high risk features as defined below who have relapsed after initial response or are refractory (failure to achieve a CR, PR, or HI) after receiving at least 4 cycles of hypomethylating agents 5-azacitidine or decitabine  $\pm$  other therapies  $\pm$  bone marrow transplant OR with *de novo* MDS but have refused to receive hypomethylating therapy:
    - 1) INT-2 or high IPSS score OR high or very high IPSS-R *or*
    - 2) Secondary MDS (defined as MDS developing in a patient with an antecedent hematologic disorder or any patient with prior chemotherapy or radiation exposure) *or*
    - 3) INT-1 IPSS or intermediate R-IPSS MDS with excess blasts ( $\geq 5\%$  blasts in BM) or transfusion-dependency *or*
    - 4) MDS progressing to oligoblastic AML with 21-30% BM blasts *or*
    - 5) CMML or MDS/MPN with  $\geq 5\%$  marrow blasts, transfusion-dependency, abnormal karyotype, or proliferative features (white blood cell count  $\geq 13,000/\mu\text{L}$ , splenomegaly on physical examination, or extramedullary disease)
5. ECOG performance status of  $\leq 2$  at study entry or Karnofsky  $\geq 60\%$  (**Appendix C**).
6. Laboratory test results within these ranges:
  - ❖ Creatinine level of 3 mg/dL or lower
  - ❖ Total bilirubin  $\leq 3$  mg/dL unless due to Gilbert's syndrome, hemolysis, or ineffective hematopoiesis
  - ❖ AST (SGOT) and ALT (SGPT)  $\leq 3$  x ULN
  - ❖ WBC  $\leq 10,000/\mu\text{L}$
7. Patients must not have received any other treatment for their disease, including hematopoietic growth factors, aside from hydroxyurea for count control, within three weeks of beginning the trial, and should have recovered from all toxicities of prior therapy (to grade 0 or 1).
8. Patients requiring hydroxyurea to bring WBC below  $10,000/\mu\text{L}$  prior to study enrollment will require a 48-hour washout prior to starting the study drug.
9. Women of childbearing potential must have a negative serum or urine pregnancy test within 72 hours prior to start of IRX5183.
10. Patients must have no clinical evidence of central nervous system (CNS) or pulmonary leukostasis,

disseminated intravascular coagulation, or CNS leukemia.

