### **2.3. Previous Cell Differentiation Therapies in Myeloid Malignancies:**

Acute promyelocytic leukemia (APL) is a prime example of success with the differentiation therapy all-trans retinoic acid (ATRA). A characteristic genetic finding in APL, the PML/RARA fusion protein, likely mediates the ability of ATRA to induce differentiation of leukemic blasts. However, it is unlikely that APL is unique among neoplastic diseases in its responsiveness to differentiation therapy. With standard induction chemotherapy and observation in patients with APL, the disease free survival at 5 years was less than 20% compared to greater than 70% DFS with ATRA induction and maintenance (Tallman et al., 2002). Thus, ATRA has become the standard of care for treatment of APL. In recent years, we have been able to completely eliminate conventional chemotherapy from the treatment of low-risk APL with the combination of ATRA and arsenic. Lo-Coco et al showed that this therapy was non-inferior to ATRA-chemotherapy, and perhaps even superior with EFS of 97% at 2 years with ATRA-arsenic versus 86% with ATRA-chemotherapy (Lo-Coco et al., 2013). Unfortunately, ATRA has had limited success in non-APL AML (Burnett et al., 2010; Burnett et al., 2007; Estey et al., 1999; Milligan et al., 2006; Schlenk et al., 2004); similarly, other differentiating agents have failed to make a major clinical impact for unclear reasons.

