### **Study Phase I:**

In the dose-escalation part of the study, we will abide by a traditional 3+3 design with 3 dose levels (dose level 1 [DL1] with 50 mg IRX5183, DL2 with 75 mg, and DL3 with 100 mg), with 1 additional dose level, DL(-1), to be only used if excessive toxicity is noted at the DL1. There will be no intra-patient dose escalation.

The first patient will enter the trial on DL1. The dose for level 1 will be a flat dose of 50 mg IRX5183 daily per the schedule above. We will enroll 3 patients at a time to determine the toxicity profile of IRX5183. If none of the 3 patients receiving DL1 experiences a DLT, another 3 patients will be treated at the next higher dose level. However, if 1 of the first 3 patients experiences a DLT, 3 more patients will be treated at the same dose level. The dose escalation will continue until at least 2 patients among a cohort of 3 to 6 patients experiences DLTs. If 2 or more patients experience a DLT on DL1, the next patient will be recruited to DL(-1). The RP2D of single agent IRX5183 will generally be the highest dose at which the DLT rate is <33% in at least six patients. If no MTD is determined, the highest dose

[figure not shown]
explored will be 100 mg. At the end of phase I, the RP2D will be determined after careful review of all of the clinical data available. The first 3 subjects enrolled to any cohort must have passed the 28 day DLT evaluation point before the 4th subject will begin treatment.

IRX5183 will be initiated at the company’s currently recommended dosage for use in APL patients of 50 mg daily (about 30 mg/m^2/day). The drug is available in 25 mg capsules, so we will be using a flat dosage. This dose of 50 mg is above the MTD of 15 mg/m^2/day from the prior phase I trial conducted in solid tumor patients. However, the DLTs seen in this trial were elevations in alkaline phosphatase in patients with known liver metastases. In addition, the phase I/II trial in patients with myeloma and lymphoma used a dose of 60 mg/m^2, which was well tolerated with no serious adverse events (SAEs). The roughly 2 months of induction therapy followed by consolidation/maintenance described above is modeled after prior studies of ATRA and other synthetic retinoids, in which it can take up to 60 days to see an initial response (Lo-Coco et al., 2013; Sanford D, 2014; Tobita et al., 1997).

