## 11. STATISTICAL CONSIDERATIONS

### 11.1. Study design & endpoints:

In the dose-escalation part of the study, there will be 3 dose levels (dose level 1 [DL1] with 50 mg, DL2 with 75 mg, and DL3 with 100 mg), with 1 additional dose level to be only used if excessive toxicity noted at the DL1. There will be no intra-patient dose escalation. Dose-escalation rules are defined through a standard 3+3 algorithm as outlined in Section 5.2.

The phase II expansion part of the study will aim to recruit a total of 27 patients with either R/R-AML or HR-MDS, and there will be an interim analysis after 13 patients for futility through a Simon two-stage minimax design based upon a Type I error rate of 0.05, power of 0.8, response probability of poor drug 0.05, and response probability of good drug of 0.2, based on prior relapsed and refractory AML trials and CTEP data on non-pediatric oncology trials from 2001 to 2012 (Itzykson et al., 2015; Ritchie et al., 2013; Thol et al., 2015; Yoko Korenaga Fukuda, 2014). Stage 1 will enroll 13 patients at the RP2D and will require at least 1 response for

continued enrollment to Stage 2, to reach the total of 27 patients. A total of 4 or more responses out of 27 patients will be considered encouraging evidence for future larger clinical trials of IRX5183.

Response will be defined per IWG criteria as CR, CRi, or PR for AML patients and as CR, CRi, PR, or HI for MDS patients (see definitions in Appendix A) and will be determined with each BM assessment. The composite of these responses across our study population will be referred to as the overall response rate (ORR). Rates of CR, CRi, PR, HI, and the composite endpoint of ORR will be summarized and reported with an exact 95% confidence interval.

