### **11.4. Sample size considerations:**

For the dose-escalation part of the trial, we will enroll up to 18 patients, per standard 3+3 design with 3 DLs (see table 2 in section 5.2). Once we have determined our RP2D, we will proceed to phase II of the trial, where we will recruit an additional 21 R/R-AML or HR-MDS patients at the RP2D, for a total sample size at the RP2D of 27 (inclusive of patients treated at the RP2D in phase I). This sample size was determined using a minimax Simon two-stage design, as described in Section 11.1. Based on prior experience at our institution in this patient population, we will account for a dropout rate of 30%, so we will aim to recruit an additional 8 patients to the dose expansion phase, so that our trial will accrue up to 35 patients to this phase.

In phase II of the trial, the study team will meet regularly to determine whether it is worthwhile to continue enrollment, if an excessive number of patients are unable to complete 2 full cycles of therapy at the RP2D, whether for reasons of DLTs or PD.

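### APL is not excluded from a trial whose rationale is non-APL disease, so a retinoid response in APL would count toward the 4 of 27 that define success

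*Combined protocol and SAP*

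**What the plan says.** **Eligibility.** Section 3.1, item 4A, admits AML by two routes. The first is "Relapsed or refractory disease after receiving one or more courses of induction chemotherapy, hypomethylating agent therapy, or bone marrow transplant". The second is de novo AML in a patient judged not to be a candidate for conventional therapy because of age, co-morbidities or preference. Neither route mentions APL, t(15;17) or PML/RARA, and the exclusion list in 3.2 does not either. Section 2.1 lists t(15;17) among the cytogenetic abnormalities of AML, so the protocol's own usage places APL inside AML.

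**Rationale.** Section 2.6 postulates that "retinoids have not been proven effective in the treatment of non-APL AML due to stromal protection by CYP26". On APL, section 2.3 says: "Thus, ATRA has become the standard of care for treatment of APL". The phase I starting dose in section 5.1 is described as the company's "currently recommended dosage for use in APL patients".

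**Decision rule.** Section 11.1 sets a Simon two-stage minimax design with "Type I error rate of 0.05, power of 0.8, response probability of poor drug 0.05, and response probability of good drug of 0.2". It states that "Stage 1 will enroll 13 patients at the RP2D and will require at least 1 response for" enrolment to go on to stage 2, and that "A total of 4 or more responses out of 27 patients will be considered encouraging evidence". Responses are combined into one overall response rate. Section 11.6 plans no stratification, section 11.7 gives subgroups for AML and MDS only, and section 11.4 counts phase I patients treated at the RP2D among the 27.

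**The concern.** The rationale and the entry criteria describe different populations. The rationale asks whether a CYP26-resistant retinoid works where retinoids have not been shown to work. The criteria also admit the one subtype that the protocol itself holds up as retinoid-sensitive. A response there would be weak evidence on the question in section 2.6, yet it would carry the same weight as any other. With a threshold of 4, one such response is a quarter of what success requires, and it is also enough to meet the only futility rule.

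There is a smaller side effect. Section 11.7 plans a qualitative comparison of outcomes in patients with and without differentiation syndrome, and section 9.2.4 calls that syndrome common in ATRA-treated APL. Even one APL patient could confound so small a comparison.

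**Working it through.** **Inputs from section 11.1.** Stage 1 has 13 patients and continues with at least 1 response. The total is 27, with success at 4 or more. The null rate is 0.05 and the target rate 0.20.

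**Inputs not in the documents (assumptions).** The APL response probability q is varied from 0.2 to 1. The number of APL patients is set at none, one or two, or is governed by a per-patient probability f. All non-APL patients respond at 0.05.

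**1. The plan's own figures.** Let X1 be the stage 1 responses (13 patients) and X2 the stage 2 responses (14 patients). Then P(success) = sum over x ≥ 1 of P(X1 = x) × P(X2 ≥ 4 − x).
- P(pass gate) at 0.05 = 1 − 0.95^13 = 0.487.
- Type I error = 0.0416; power at 0.20 = 0.801.
- A search for the smallest total sample size meeting 0.05 and 0.80 returns this same design. The plan's arithmetic is right.

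**2. One APL patient in stage 1.** X1 becomes Binomial(12, 0.05) plus Bernoulli(q), and P(pass gate) = 1 − 0.95^12 × (1 − q), with 0.95^12 = 0.540.

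| q | P(pass gate) | Type I error, non-APL question |
|---|---|---|
| 0.2 | 0.568 | 0.057 |
| 0.5 | 0.730 | 0.088 |
| 0.8 | 0.892 | 0.118 |
| 0.9 | 0.946 | 0.128 |
| 1 | 1.000 | 0.139 |

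The type I error is linear in q. It is 0.0416 at q = 0.05 and 0.1386 at q = 1, so the slope is 0.0970 / 0.95 = 0.102. It therefore crosses 0.05 at q = 0.05 + (0.0500 − 0.0416) / 0.102, or about 0.13.

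**3. Gate or final count?**
- Suppose a certain APL responder opens the gate but is not counted toward the 4. Success then needs 4 or more among 26 others at 0.05, which has probability 0.039. That is no inflation.
- Put the certain responder in stage 2, where it cannot affect the gate (still 0.487). Type I error is 0.126, against 0.139 in stage 1. At q = 0.5 the pair is 0.082 and 0.088.
- Dropping the gate altogether gives only P(4 or more of 27) = 0.044 under the null.

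Most of the inflation therefore comes from counting the response toward the final 4.

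**4. Two APL patients in stage 1.** Type I error is 0.161 at q = 0.5 and 0.313 at q = 0.9.

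**5. Allowing for the chance that no APL patient enrols.** If each patient has APL with probability f, the effective null rate is 0.05(1 − f) + fq. For f = 0.01 it is 0.0545 at q = 0.5 and 0.0585 at q = 0.9, giving type I error of 0.054 and 0.067. The chance of any APL patient among 27 is then 1 − 0.99^27 = 0.24. For f = 0.02 the range is 0.069 to 0.099.

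**The case against.** **Other entry rules already narrow the door.** Section 3.2 bars retinoids in the previous 3 months and allows exclusion of any condition that would confound interpretation of the data. Section 3.1 bars clinical disseminated intravascular coagulation. The first AML route requires prior induction chemotherapy, hypomethylating therapy or transplant, which a patient treated only with ATRA and arsenic would not have had. The second requires that conventional therapy be unsuitable or declined, which should be uncommon in APL. This stands as far as it goes: enrolment of APL is probably rare. But the confounding clause is discretionary and does not name APL. A patient with relapsed APL after chemotherapy, more than 3 months off a retinoid and without clinical coagulopathy, meets the criteria.

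**The statistical section never says non-APL.** The objectives and the endpoint refer to relapsed or refractory AML and high-risk MDS. Section 11.1 bases the response probabilities on prior relapsed and refractory AML trials and CTEP data. A reader might infer that the 5% null was set for retinoids in non-APL disease, but the documents do not say so. The error rates above are therefore false-positive rates for the question in section 2.6, not for a hypothesis written into section 11.

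**An APL response is not assured.** The likely entrant has relapsed, often after ATRA, and section 2.5 describes ATRA resistance. No figure in the documents supports a particular q. This stands, and it is why a range is shown.

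**Conclusion.** The gap is real: APL is eligible as written, the rationale is about non-APL disease, and no part of the analysis separates the two. Confidence in that is high.

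Confidence in the size is low, because it depends on two quantities that the documents do not supply. If an APL patient enrols, the error exceeds the nominal 0.05 in stage 1 for any assumed response rate above about 0.13. If APL is rare at about 1% per patient, the unconditional error is only slightly above nominal.

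Two stronger readings are tempting and unsupported. One is that the trial's error rate simply is 0.118 or more; that holds only given an APL patient in stage 1 and an assumed response rate of 0.8 or higher. The other is that the 1-of-13 gate drives the inflation; one responder does satisfy it, but opening the gate without adding to the final count leaves the error at 0.039. The Simon design itself needs no change.

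**What to change.** Add APL, defined by t(15;17) or PML-RARA, to the exclusions in section 3.2. If the sponsor wants APL to remain eligible, or has already treated such patients, state in sections 11.1 and 11.8.2 that they are left out of both the 13 and the 27, including any treated at the RP2D in phase I, and report their responses separately.

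Either route restores the planned 0.042 type I error and 0.801 power with the total still at 27. The cost is one eligibility line or one analysis-population sentence. Accrual loss should be negligible if APL is as uncommon here as the entry rules suggest; keeping APL eligible but uncounted would mean replacing each such patient in the count.
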